Official Title: Delayed Rewarming for Neuroprotection in Infants
Following Cardiopulmonary Bypass Surgery

NCT03036072

Document Date: 08/31/2017

Delayed Rewarming for Neuroprotection in Infants Following Cardiopulmonary Bypass Surgery: A Safety Study

[name].

INTRODUCTION

Therapeutic hypothermia (TH) is a medical treatment used for neuroprotection in certain clinical scenarios where there is a substantial risk of brain injury. TH is thought to improve neurological outcome by decreasing cerebral metabolism, reducing blood-brain barrier disruption and attenuating free-radical mediated and excitatory neurotransmitter-mediated pathology. TH during cardiac surgery has been in routine use since the 1950's and is also considered a recommended treatment for adults who have experienced cardiac arrest according to both the American Heart Association (AHA) and the International Liaison Committee on Resuscitation (ILCOR) guidelines. Amongst adult cardiac arrest patients, there has been recent controversy regarding whether hypothermia (cooling to 33°) or the avoidance of **hyperthermia** (aggressive maintenance of 36°) provides superior neuroprotection. A recent publication in the New England Journal of Medicine of 939 adults with out-of-hospital cardiac arrest did not show a difference in survival or neurological outcome between these two management strategies¹. While the depth and duration of TH remains controversial in adult patients, use of therapeutic hypothermia in newborn infants with moderate to severe encephalopathy and signs of intrapartum asphyxia is considered the current standard of care, with multiple pilot studies demonstrating safety^{2,3} and multiple additional randomized control trials demonstrating efficacy⁴⁻⁶. Eleven randomized trials comprising more than 1500 infants were evaluated in a Cochrane review on this subject and use of TH resulted in a "statistically significant and clinically important reduction in the combined outcome of mortality and major neurodevelopmental disability to 18 months of age."⁷ The proposed research project will focus on the use of TH and the management of rewarming after TH in infants with congenital heart disease (CHD) following congenital heart surgery. Despite significant advances in surgical approaches to CHD, developmental outcomes for the 40,000 affected infants born each year remain disproportionately poor^{8,9}. Following congenital heart surgery, infants demonstrate lower than expected intelligence quotients, hypotonia, microcephaly, language delay and poor functional outcomes with less independence in daily activities compared to typical peers¹⁰⁻¹². These suboptimal developmental outcomes are the rationale for reassessing the current standard of care.

BACKGROUND AND HYPOTHESIS

At Maine Medical Center, TH is routinely employed for 24 hours in the care of adult patients with cardiac arrest and for 72 hours in newborns with signs of intrapartum asphyxia. Both these patient populations are slowly "rewarmed" (brought back to normothermia) over a period of 12 hours in a carefully controlled manner. This strategy for slow rewarming was developed due to the re-emergence of seizures, a clinical sign of brain irritability and injury, in infants more rapidly rewarmed over 6 hours¹³⁻¹⁵. Patients who undergo cardiac surgery (adults, children and infants) however, are typically rapidly "rewarmed" to normothermia at a rate of 1°C each 3-5 minutes, due to concerns surrounding the risks associated with prolonged time on the cardiopulmonary bypass machine, such as higher rates of thrombus formation, embolic events or even hemorrhages. For an infant cooled to 18°C during surgery, it may take only 54 minutes to rewarm to 36°C.

There is emerging evidence that rapid temperature changes of this magnitude may be deleterious to the very neurons that TH is being employed to protect. Animal data suggest that such rapid rates of rewarming may diminish or even negate the neuroprotective effect of hypothermia used during surgery^{16,17}. In human trials, adults and children have demonstrated significant cognitive deterioration if rapidly rewarmed to normothermia on cardiopulmonary bypass^{18,19}. These studies have used a combination of serum biomarkers (s100b and Neuron Specific Enolase) that are indicative of brain injury and performance on cognitive testing as outcome variables.

S100b is a glial-derived calcium binding protein that is a biomarker for brain injury in multiple populations, including adult patients with traumatic brain injury and stroke and neonates with hypoxic ischemic brain injury²⁰. S100b has also been studied in adults and children following cardiopulmonary bypass²¹⁻²³ and found to be elevated with correlations established between poorer neurological outcomes and elevated s100b levels. Neuron specific enolase (NSE)²⁴ is a glycolytic enzyme concentrated in the cytoplasm of neurons and another biomarker of cerebral injury that can be easily measured like s100b from a serum sample. Both s100b and NSE were assessed in term encephalopathic newborns treated with TH and were found to be associated with developmental outcome at 15 months with higher levels of either biomarker reflecting poorer developmental outcome²⁵. S100b as a biomarker has also been assessed in children with congenital heart disease in the post-operative setting. In a 2013 study, 80 children ages 6-15 years, who received surgery for correction of a common congenital heart defect, were treated with either the standard of care (rapid rewarming to normothermia in the operating room on bypass) versus a delayed rewarming technique (which stopped rewarming on bypass at 33°C and permitted passive rewarming to normothermia over the next several hours)¹⁹. The children in the delayed rewarming group had lower s100b levels in the postoperative setting compared to the standard of care group. In addition, the delayed rewarming group showed no post-operative deterioration in neuropsychological function compared to the standard of care group, which displayed post-operative deterioration across all domains including information, comprehension, arithmetic, digit span and verbal IQ. These findings in older children are compelling and suggest that similar investigation is needed in infants.

In this proposed pilot study, the safety of delayed rewarming will be assessed in infants under the age of 12 months who require cardiopulmonary bypass surgery for repair of congenital heart defects. **It is proposed that the delayed rewarming technique will be safe and that a trend toward lower serum biomarker levels will be seen in the experimental group compared to the standard of care group.** Successful completion of this pilot safety study will lay the foundation for a future adequately powered efficacy study to determine if the delayed rewarming technique leads to improved developmental outcomes.

Specific Aim 1: Evaluate safety of delayed rewarming in infants following congenital heart disease surgery through intensive care unit level monitoring of parameters including hemodynamic status, coagulopathy, infection, hyperthermia and subcutaneous fat necrosis. In this pilot study, infants under the age of 12 months with congenital heart disease requiring surgical palliation with cardiopulmonary bypass will be randomly assigned to the standard of care versus experimental group. The experimental treatment is “delayed rewarming” and will be defined as the cessation of rewarming on cardiopulmonary bypass at 35°C. There will be 12 hours of controlled rewarming to 36.5°C via the use of a programmable body temperature regulating blanket that is FDA approved for this use. Safety will be determined by continuous close monitoring in the post-operative setting in the Pediatric Intensive Care Unit for adverse effects on hemodynamic status (bradycardia, junctional ectopic tachycardia, hypotension and need for additional medication to support heart rate or blood pressure), for coagulopathy (lab evidence of disseminated intravascular coagulation, chest tube output and need for transfusion of blood products), infection (such as pneumonia), effects on other end organs (monitored via lab testing for kidney function daily), frequency of infants with **hyperthermia** and lastly close inspection of the skin to insure there is no evidence for subcutaneous fat necrosis. My hypothesis is that the “delayed rewarming” group will not demonstrate a higher frequency or severity of adverse events compared to the standard of care group.

Specific Aim 2: Compare early and late biomarkers for adverse developmental outcomes between standard of care and “delayed rewarming” groups including serum biomarkers of brain injury, electroencephalogram (EEG) and developmental outcomes.

2.1 Compare levels of serum biomarkers of brain injury in the acute post-operative setting including serum s100b and NSE (neuron specific enolase). Levels will be assessed in both groups in the pre-operative setting for baseline and

serially in the post-operative setting for 72 hours. It is hypothesized that infants in the “delayed rewarming” group will show a trend toward lower levels of biomarkers of brain injury.

[figure not shown]
2.2 Record EEG and monitor seizure frequency in infants for 48 hours following CHD surgery. Seizures, if they occur, will be treated in both groups and the duration quantified in seconds. EEG is needed primarily to rule out potential confounding effects of seizures on later developmental outcome. It is hypothesized that there will be infrequent seizures and no differences in seizure frequency or duration between groups.

2.3 Compare developmental outcomes using Bayley Scales of Infant Development (Bayley 3). Bayley testing will be performed on infants at either 6 or 12 months of age depending on the infant’s age at the time of surgery. It is hypothesized that infants in the “delayed rewarming” group will show a trend toward improved Bayley scores compared to the standard of care group.

Preliminary data:

A retrospective review of cases of congenital heart disease requiring surgical palliation was performed for cases from January 2011 to May 2014. The database was provided by [name] to [name] for the purposes of this analysis. This database is kept for quality work in [name] office. Please see the attached letter of support for this project from [name]. In this review, there were 191 surgeries performed on infants under the age of 12 months by [name] in the 41 month interval (average 4.6 surgeries per month). Some infants required multiple surgeries and therefore the total number of surgeries (191) reflects 119 individual infants. The proposed research project includes only infants undergoing cardiopulmonary bypass (CPB) for the first time. In this sample, there were 88 CPB surgeries. Ten infants had surgery requiring CPB on more than one occasion and thus eliminating repeat exposures to cardiopulmonary bypass, 76 of the 88 total surgeries would have met inclusion criteria for enrollment into this research project (1.9 infants per month or 22 per year). Anticipating a 2 year period of recruitment, there should be approximately 44 eligible infants and we will seek to enroll 30.

[figure not shown]

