Figure 3b: Research design for KL2 project

Randomization: We will randomize in a one to one fashion. A random number generator will be used with those numbers being translated into a list of sequentially numbered opaque envelopes that will be opened by the principal investigator (PI) in order at the time of randomization following the informed consent process.

Recruitment: [name] and [name] are pediatric cardiologists and follow expectant mothers weekly or biweekly throughout a pregnancy known to be complicated by a diagnosis of congenital

heart disease. [name] and [name] will refer appropriate patients to [name] (PI) for consideration of enrollment. The PI will meet with the pregnant mother and father in the outpatient setting several weeks after the diagnosis has been made, giving the family time to come to terms with this new diagnosis. At the first meeting with the PI, the family will be informed about the research study and given informational handouts. Another meeting will occur prior to the admission during which the congenital heart surgery will be performed. At this second meeting, informed consent documentation will be reviewed and signatures obtained from parents willing to participate. For infants who need congenital heart surgery within the first few days of life or for those in whom a fetal diagnosis was not made, the PI will obtain informed consent from parents in the hospital prior to surgery. The envelopes for randomization will be opened at the time consent is obtained to insure that there is adequate time to arrange for the type of post-operative care the infant will receive (intervention versus standard of care).

Standard of care group: For infants assigned to the standard of care group, the congenital heart surgery will be performed according to usual practice with the degree of intra-operative hypothermia determined by the cardiothoracic surgeon and his team based on the anticipated complexity of the case. Following completion of the surgical procedure, the infant will be rapidly rewarmed on cardiopulmonary bypass at a rate of 1°C each 3-5 minutes. The infant will achieve normothermia of 36-37°C and be transported to the Pediatric Intensive Care Unit (PICU) for routine post-operative monitoring. Standard of care procedure in the post-operative setting is clearly defined below on Figure 4.

Figure 4: Standard of Care Temperature Management after Bypass

LOCATION	PERSON RESPONSIBLE	RECORDING SITE	GOAL TEMP	FACTORS

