Experimental group: For infants assigned to the experimental group, the congenital heart surgery will be performed according to usual practice as detailed in the standard of care group section above, with depth of hypothermia dictated by the complexity of the congenital heart lesion to be repaired. Upon completion of the surgical procedure, partial rewarming will occur on cardiopulmonary bypass, but will stop when the infant reaches 35°C.

The infant will be transported from the operating room to the PICU at 35°C and placed on a servo-controlled blanket with an esophageal temperature probe placed. Through use of the servo-controlled blanket, the rate of rewarming will be carefully regulated with increases in temperature of 0.3°C every 2 hours for 6 and then of 0.2°C every 2 hours for 6 hours to the goal temperature of 36.5°C (see Appendix 1 for temperature management worksheet phase 1). The intensity and frequency of post-operative monitoring will be exactly the same in the experimental group as in standard of care group, including post-operative EEG, serum biomarker testing and neurodevelopmental follow up. The following parameters will be observed in the experimental group and compared with the standard of care group.

1. Hemodynamic status-Infants who are hypothermic typically have lower resting heart rates than those who are normothermic (80-100 beats per minute versus 120-140 beats per minute respectively). In the post-operative congenital heart infant, bradycardia (slow heart rate) could conceivably have an adverse impact on the hemodynamic status of the infant and if untreated this could also impact renal function. Hemodynamic status will be continuously monitored in the same manner as detailed in the standard of care section. Intravenous medications to support cardiac function and blood pressure (which these infants are typically already treated with) will be up-titrated if necessary. The need for permanent pacemaker implantation will be documented.

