In order to carefully define what is considered an adverse event, a retrospective chart review was performed for 15 infants in the past 12 months who survived congenital heart surgery with cardiopulmonary bypass at MMC. Of the 15 infants, the mean age at the time of surgery was 148 days with a range from 4 to 356. Of the 15 infants, 10 were male and 5 female. These infants had a mix of cardiac lesions similar to those who would be enrolled in this study. See Table 1 for a full outline of parameters that will be considered acceptable for infants enrolled in the study, which are based on the retrospective review of 15 survivors. Using these parameters to define what has been previously consistent with “safe”, any infant enrolled in the proposed study with results outside these parameters will then be considered as an adverse event and the data safety monitoring board will be informed. If a severe adverse event occurs in either Phase 1 or Phase 2 of the proposed research protocol, no additional infants will be enrolled and all experimental exposures will be suspended until a decision is made by the DSMB.

Table 1: Definitions of Serious, Moderate and Other Adverse Events

Serious Adverse Events	Reported to DSMB within 24 hours of occurrence
Mortality	Death within 48 hour period following surgery
Need for resuscitation	Need for cardiopulmonary resuscitation within 48 hours of surgery
ECMO after surgery	Persistent need for bypass (ECMO) following surgery; STUDY EXCLUSION CRITERIA
Return to OR on day of surgery	Unexplained hemorrhage prompting return to the OR for exploratory surgery
Stroke or seizures	Ischemic or hemorrhagic stroke OR status epilepticus OR clinical or electrographic seizures
Moderate Adverse Events	Reported to DSMB within 48 hours of occurrence
Bradycardia	Clinically significant heart rate <100 bpm for >30 minutes*
Tachycardia	Clinically significant heart rate > 160 bpm for 30 minutes*
Arrhythmia (JET)	Any occurrence of JET(Junctional ectopic tachycardia) OR other arrhythmia
Hypotension	Systolic BP< 70 mm Hg OR Diastolic BP< 30 mm Hg *
Coagulopathy	INR > 2.2 OR PTT > 74 seconds Thrombocytopenia with platelets < 50,000 Chest tube output more than 5 cc/kg/hr OR 40 cc/kg in an 8 hour shift
Leukopenia	White blood cell count < 4,000
Other adverse Events	Reported to DSMB within 7 days

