Data will be collected at the bedside and through chart review. A study ID number will be assigned to each infant and study documents will all use this ID number to combine data. Identifiable data will be stored separately. Preoperative (baseline) variables including gender, age in months and type of congenital heart lesion will be collected. A baseline s100b and NSE will also be considered pre-operative variables. Intraoperative variables including aortic cross clamp time, cardiopulmonary bypass time, lowest temperature during surgery, time for rewarming on bypass in all 3 groups and s100b and NSE at the completion of cardiopulmonary bypass will be collected. Postoperative variables include temperature, heart rate, blood

pressure, presence or absence of an arrhythmia such as JET, pressor use, frequency of transfusions, hours of intubation, coagulation dysfunction, frequency and type of infection and presence or absence of subcutaneous fat necrosis for 48 hours after surgery. S100b and NSE will be compared at the 4 post-operative time points as well.

Success of randomization will be assessed by comparing baseline characteristics in the two treatment groups; we acknowledge that randomization may not be entirely effective with such a small sample size and we will examine the data for biases to be considered in interpreting our findings. For this safety study, primary outcomes will be composite outcomes and will include the frequency of serious adverse events as well as the frequency of any adverse events (see Table 1) and will be compared among treatment groups using chi square tests or Fisher's exact tests, as appropriate. The frequency of individual adverse events such as hemodynamic compromise, arrhythmia, coagulopathy, infection, hyperthermia and subcutaneous fat necrosis will also be examined. Biomarkers (s100b and NSE) will be examined using a repeated measures analysis of variance, with the time * treatment interaction serving as the hypothesis test.

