Sources of Materials: For this protocol, the frequency of adverse events will be compared between the standard of care group and the experimental group across 5 specific areas as follows: hemodynamic status, coagulopathy, infection, hyperthermia and subcutaneous fat necrosis (see next section for full details). The current standard of care for intensive care unit monitoring is adequate to monitor for adverse events in both the standard of care and experimental groups. Adverse events will be clinically apparent and both the event and medical management will be documented in the infant’s medical record. Continuous vital signs (temperature, heart rate, blood pressure, respiratory rate and oxygen saturation) will be monitored and recorded by the nurse caring for the patient as well as all usual standard post-operative laboratory and imaging studies. These will include laboratory tests for evidence of renal dysfunction, coagulation studies and chest x-rays monitoring for infection and fluid accumulation. The equipment used to provide delayed rewarming to the 15 infants in the experimental group will be purchased by the research study.

In order to protect the subject information described above, HIPAA standards will be adhered to and data that is kept will be de-identified. Each participant will be assigned an individual participant number and names and medical records will not be used. All paper documentation will be kept in a secure file in a locked area and will ultimately be scanned to pdf and stored on a secure and encrypted server. When

creating the REDCap data base, the subject number will be used as the principal identifier. [name] and her Research Coordinator, [name] will be the only persons with access to the key which encodes the subject name with the demographic and other information.

Potential Risks: There are potential risks to the critically ill subjects enrolled in this study, the most significant of which are outlined below:

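### The arms diverge in the operating room, but moderate or transient harms before PICU arrival have no defined collection and the start of the adverse-event window is not stated

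*Combined protocol and SAP*

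**What the plan says.** **Where the arms part.** The Experimental group section says that "partial rewarming will occur on cardiopulmonary bypass, but will stop when the infant reaches 35°C", and then: "The infant will be transported from the operating room to the PICU at 35°C". Under Standard of care group, control infants are "rapidly rewarmed on cardiopulmonary bypass at a rate of 1°C each 3-5 minutes" until they reach 36-37°C, and only then are they transported.

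**Where safety is observed.** Specific Aim 1 places it after surgery in intensive care: "Safety will be determined by continuous close monitoring in the post-operative setting in the Pediatric Intensive Care Unit for adverse effects on hemodynamic status". Sources of Materials adds: "The current standard of care for intensive care unit monitoring is adequate to monitor for adverse events". It names the nurse caring for the infant as the recorder of vital signs.

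**What is recorded.** ANALYSIS lists "Intraoperative variables including aortic cross clamp time, cardiopulmonary bypass time, lowest temperature during surgery", then rewarming time on bypass and the end-of-bypass biomarkers. Heart rate, blood pressure, arrhythmia, pressors, transfusions and coagulation appear only in the postoperative list, which runs for 48 hours after surgery.

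**What counts as an event.** Table 1 defines mortality as "Death within 48 hour period following surgery". It uses a similar clock for resuscitation, and includes ECMO and a same-day return to the operating room for hemorrhage. Its moderate rows (heart rate, arrhythmia, hypotension, coagulopathy, leukopenia) give neither a location nor a start time.

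**How the post-operative setting is used.** The Standard of care group section introduces Figure 4 as the procedure for that setting. Figure 4 has three locations: operating room, transport and PICU.

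**The concern.** The primary outcomes are the frequencies of serious and of any adverse events by arm. A safety comparison should begin when the assigned treatments begin to differ, and here that is on bypass. Separation from bypass, hemostasis and transport all take place at different assigned temperatures, and the protocol itself treats bradycardia, arrhythmia and coagulopathy as possibly temperature-related.

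If collection in practice starts at the PICU door, an episode that arises and resolves before arrival is counted in neither arm. The pilot's conclusion on safety would then cover only part of the treated period, without saying so. Two site staff could also read the window differently, because Aim 1 names the PICU while Figure 4 extends the post-operative setting back to the operating room.

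**Working it through.** **1. The plan's own figure.** Background gives 1°C per 3-5 minutes and 54 minutes from 18°C to 36°C. (36 − 18) × 3 = 54 minutes, which reproduces it at the fast end of the rate. The slow end gives 18 × 5 = 90 minutes.

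**2. The contrast when rewarming stops.** 36 − 35 = 1°C and 37 − 35 = 2°C, so the planned gap is 1-2°C. At the stated rate the experimental arm has 1 × 3 = 3 to 2 × 5 = 10 minutes less rewarming on bypass. The recorded bypass and rewarming times can show those minutes, but not a harm.

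**3. The contrast at PICU arrival.** Experimental infants arrive at 35°C, and the control goal in the PICU (Figure 4) is still 36-37°C. The planned gap is again 1-2°C, so it is no larger before arrival than at arrival.

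**4. Exposure below the 36.5°C goal in the experimental arm.** The schedule is +0.3°C every 2 hours for 6 hours, then +0.2°C every 2 hours for 6 hours.
- Linear: 6 × (1.5 + 0.6)/2 + 6 × 0.6/2 = 6.3 + 1.8 = 8.1 degree-hours.
- In two-hour steps: 2 × (1.5 + 1.2 + 0.9 + 0.6 + 0.4 + 0.2) = 9.6 degree-hours.
- The time *t* from the end of bypass rewarming to PICU arrival is not given; 0.5-2 hours is assumed. Share before arrival = 1.5*t* / (1.5*t* + total).

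| *t* (assumed) | Degree-hours before arrival | Share, steps (9.6) | Share, linear (8.1) |
|---|---|---|---|
| 0.5 h | 0.75 | 7% | 8% |
| 1 h | 1.5 | 14% | 16% |
| 2 h | 3.0 | 24% | 27% |

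This measures exposure. It does not estimate missed events.

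**5. Sensitivity to small counts.** With 15 per arm, two-sided Fisher's exact p for *k* versus 0 events is 2 × C(15,*k*)/C(30,*k*).
- *k* = 5: 2 × 3,003/142,506 = 0.042.
- *k* = 4: 2 × 1,365/27,405 = 0.100.

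One uncounted infant can move the result across 0.05 (a conventional level; the plan states none).

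**6. What the plan provides for an event before PICU arrival.**

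| Event | Provision |
|---|---|
| Death, resuscitation | Serious rows in Table 1; clock tied to surgery, start not stated |
| ECMO | Serious row, but the same row also labels it an exclusion |
| Bleeding | Serious row requires a return to the operating room; moderate row uses laboratory values and chest tube output |
| Transfusion | Postoperative variable; no Table 1 row |
| JET, other arrhythmia, bradycardia, hypotension | Moderate rows without a location; data items listed as postoperative only |
| Return to bypass after first separation | No row short of ECMO; bypass time recorded |

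**The case against.** The strongest reply is that the protocol's post-operative period already includes the operating room and transport. Figure 4 covers both, rewarming is described as following completion of the procedure, and the end-of-bypass blood sample is called post-operative. Table 1 has no location limit, and the text before it counts any enrolled infant with results outside its parameters. ANALYSIS allows chart review. The Data Safety and Monitoring Plan lets any care provider report an event and has a coordinator check data against source documents and oversee adverse-event monitoring. Figures 3a and 3b and the attached DSMB plan cannot be seen, so nothing can be inferred from them.

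Most of this stands. It rules out the stronger reading that harms before PICU arrival are simply not collected: severe events are partly covered, and a persisting problem would still be seen in the PICU. It does not close the gap. Aim 1 and Sources of Materials point to intensive care, no listed data item would supply operating-room or transport events, and optional reporting is not systematic collection in both arms.

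A reader might also infer two further things that the documents do not support:
- *That the temperature gap is largest before PICU arrival.* Step 3 shows the same planned 1-2°C at arrival.
- *That missed events must bias the comparison toward a finding of safety.* That is plausible but not shown. The protocol looks for less JET with delayed rewarming, so lost events could equally fall in the control arm.

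**Conclusion.** The point holds as a gap in definition and collection, and it should be corrected. The treatment contrast starts in the operating room. Moderate or transient harms from then until PICU arrival have no systematic collection in both arms, and it is unclear whether the 48-hour windows include that interval. Severe events are partly covered by Table 1.

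The size in events is unknown, because the documents give neither event rates nor the length of the interval. The 7-27% share illustrates exposure only and rests on the assumed 0.5-2 hours and on infants staying at 35°C until arrival. The plan already concedes that 15 per arm cannot support definitive analysis, so what is at stake is how complete the safety description is, more than any single test.

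**What to change.** - State in Aim 1, Table 1 and ANALYSIS that the adverse-event window opens, in both arms, when rewarming on bypass stops, and closes at the same elapsed time after that point.
- Abstract the anesthesia and perfusion records (assumed to be kept routinely) up to PICU arrival for events that meet the existing Table 1 definitions. Count these in the composites by randomized arm, and tabulate the operating-room/transport and PICU periods separately.
- Report operating-room blood products, bleeding and return to bypass descriptively by arm. Do not add them to the primary composites: Table 1 has no operating-room threshold for them, and counting any occurrence could bring the any-event composite close to saturation in both arms.
- Reconcile the ECMO row, which is both a serious event and an exclusion, so that it is clear whether such an infant stays in the count.

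The cost is a few sentences of wording and some record abstraction for 30 infants, with no change to care. The background event count will rise in both arms. The protocol itself notes that anticoagulants used during bypass contribute to early coagulation problems, which is one reason to show the two periods separately.
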